APPENDIX: Drug Shipment to Patients

- 1. When study medication is given to the coordinator, the hand packaging and labeling process will begin.
- 2. Study drugs need to be kept in a temperature range of 68°F to 77°F at all times, so to ship study medications we must prepare them with adequate ice packs and a Styrofoam box.
- 3. You can purchase the Styrofoam box and Ice Gel Pack on Amazon, which have the picture below and are very inexpensive.

- 4. Please ensure you keep the ice pack in a 68°F to 77°F temperature location at least 24 hours prior to shipment of drug.
- 5. Once the packaging is completed, prior to sending it to Fedex or UPS please ensure "UN3373 Biological Substance Category B" Labels/Stickers are attached on the box.
- 6. Once shipment is ready, you may contact UPS or Fedex via the internal mail office within institute. Please be sure that your shipment is by over-night shipping.
- 7. Once the study drugs are delivered to the participant, the study coordinator is required to contact participants to ensure study drugs were received and are not damaged.

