B.6. Patient Withdrawal

A patient has the right to withdraw from the study at any time, for any reason, and without repercussion. The investigator has the right to withdraw a patient from the study in the event of an intercurrent illness, adverse event, treatment failure, protocol violation, cure, and for administrative or other reasons. An excessive rate of withdrawals would render the study uninterpretable; therefore, unnecessary withdrawal of patients will be avoided. Should a patient (or a patient's legally authorized guardian or representative) decide to withdraw, all efforts will be made to complete and report observations as thoroughly as possible. Early termination procedures will be followed.

B.7. Patient Replacement

Patients prematurely withdrawn from the study can be replaced, if needed, to ensure an adequate number of evaluable patients. The investigator, (in cooperation with the study statistician, if applicable) will decide whether or not to replace withdrawn patients.

B.8. Investigation Drug Management

At each study site, the drug management will be performed by their respective Investigational Drug Services (IDS). Study drug will be refrigerated at the site at a temperature of 2 to 8°C; refrigerator temperature will be logged daily. At no time, will product be left unattended or outside the control of an individual knowledgeable with regard to product temperature requirements. Moreover, no one will administer product that has not been maintained according to temperature requirements. Study drug will be shipped at a temperature of 2 to 8°C to the investigator or designee at regular intervals or as needed during the study. During site close-out, and following drug reconciliation and documentation, all opened and unopened vials of study drug will be kept current. The primary investigator will account for all opened and unopened vials of study drug. These records will contain the dates, quantity, and study medication:

- a) dispensed to each patient,
- b) returned from each patient (if applicable), and
- c) disposed of at the site or returned to Amgen Inc. or designee

All accountability records will be made available for inspection by regulatory agency inspectors.

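### The patient-shipment appendix sets a room-temperature range for study drug without limiting it to transit, which conflicts with the 2 to 8°C rule in B.8, and it gives no maximum time out of refrigeration

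*Combined protocol and SAP*

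**What the plan says.** Section B.8 of the combined protocol and SAP covers drug management at the sites. On storage it says: "Study drug will be refrigerated at the site at a temperature of 2 to 8°C; refrigerator temperature will be logged daily". On supply to the sites it says: "Study drug will be shipped at a temperature of 2 to 8°C to the investigator or designee". It also sets a rule on use: "no one will administer product that has not been maintained according to temperature requirements". For shipment to patients B.8 gives no temperature and refers to the Appendix.

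The Appendix on drug shipment to patients gives the packing steps:

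- Item 2: "Study drugs need to be kept in a temperature range of 68°F to 77°F at all times".
- Item 4: "Please ensure you keep the ice pack in a 68°F to 77°F temperature location at least 24 hours prior to shipment of drug".
- Item 6: "Please be sure that your shipment is by over-night shipping".
- Item 7, after delivery: "the study coordinator is required to contact participants to ensure study drugs were received and are not damaged".

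Neither text states how long drug may stay outside 2 to 8°C. The accountability records described in B.8 cover dates, quantities and study medication, and list no temperature item.

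**The concern.** Repatha is the only study treatment, and every patient receives it. The plan gives two temperature ranges for the same product, and the second is not confined to a stage of handling. A coordinator at one of up to 8 centers who reads item 2 literally finds that drug taken from the site refrigerator has already failed it.

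The practical stake is the rule on use in B.8. Suppose a parcel is delayed beyond one night. The coordinator then needs a stated limit to decide whether the supply may be used, and the plan gives none. The follow-up call asks only about receipt and damage. The monitoring in E.11 and the inspections in E.12 look at existing records and storage conditions, so neither creates a transit record. An over-long delivery could pass every written check, and A.3 says that patients inject the drug themselves.

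**Working it through.** **Inputs.** B.8: 2 to 8°C. Appendix items 2 and 4: 68 to 77°F. B.3: one dose every 2 weeks, 39 doses. B.2: 150 patients, 78 weeks. B.8: drug given at baseline and then preferably every 6 months.

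**Step 1: common units.**

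- °C = (°F − 32) / 1.8. (68 − 32) / 1.8 = 20.0°C and (77 − 32) / 1.8 = 25.0°C.
- °F = 1.8 × °C + 32. 1.8 × 2 + 32 = 35.6°F and 1.8 × 8 + 32 = 46.4°F.
- Distance between the ranges: 20 − 8 = 12°C, or 68 − 46.4 = 21.6°F. The overlap is nil.

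**Step 2: the text, leg by leg.**

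- Supply to the site: 2 to 8°C (B.8).
- Storage at the site: 2 to 8°C, logged daily (B.8).
- Shipment to the patient: no range in B.8. The Appendix gives 20 to 25°C, worded without limit to this leg, and asks for overnight shipping. No maximum time outside 2 to 8°C is given.
- Receipt by the patient: the call covers arrival and damage only.

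Item 4 governs the packs, not the drug, but it confirms that item 2 is not a misprint for a cold range: packs held at 20 to 25°C cannot keep drug at 2 to 8°C.

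**Step 3: what the rule on use then means.** B.8 refers to temperature requirements without defining them for the patient leg. There are three readings:

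- If item 2 applies literally, drug refrigerated at the site fails it.
- If 2 to 8°C applies throughout, drug packed under the Appendix fails it.
- If each leg has its own range, there is no conflict. The plan does not say this, and the patient leg still has no time limit.

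**Step 4: how many doses pass through the instruction.** At 6-month intervals, 78 / 26 = 3 supplies and 39 / 3 = 13 pens per supply. The first is given at the baseline visit, which leaves 2 resupplies, or 26 pens. B.9 has only two in-person visits, so resupplies do not coincide with a scheduled visit. The share c that is couriered is not documented, so a range is shown. Doses per patient = 26c; shipments = 2 × 150 × c, before withdrawals.

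- c = 0: 0 of 39 doses, 0 shipments.
- c = 0.5: 13 of 39 (33%), 150 shipments.
- c = 1: 26 of 39 (67%), 300 shipments.

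These count doses handled under the unclear instruction, not doses shown to be affected. The 6-month interval is a preference in B.8, so the counts hold for that interval only.

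**The case against.** The strongest reply is that the two ranges govern different legs. B.8 ties 2 to 8°C to site storage and to shipment to the investigator, then hands the patient leg to the Appendix. Item 2 runs straight on to how to pack a parcel, so in context it reads as a packing instruction. A coordinator who refrigerates at the site and then packs at room temperature breaks nothing written for the patient leg. Overnight shipping keeps the expected transit short. The prescribing information may also allow a period at room temperature, in which case the defect is mostly loose wording.

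Much of this stands. The sequential reading is plausible and may well be what was meant, and overnight shipping is a real control. But item 2 does not limit itself to transit, and asking for an overnight service does not say what to do with a parcel that takes longer. If the prescribing information permits a period at room temperature, the plan should state that period.

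A reader might infer more than the documents support:

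- That no parcel can be packed in compliance with the plan. This goes too far, since only one range is written for the patient leg.
- That B.8 forbids any supply leaving the site, from the sentence "At no time, will product be left unattended or outside the control of an individual knowledgeable with regard to product temperature requirements". B.8 is framed around each study site, and that literal reading would rule out the self-injection the plan intends.
- That shipped drug lost potency, or that the trial lost power. Nothing in the documents shows an excursion or its effect.

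**Conclusion.** The point holds as an inconsistency in the handling rules for the only study drug. Item 2, as worded, is wrong for drug that B.8 has refrigerated: the ranges are 12°C (21.6°F) apart. If room-temperature transit is intended, the plan neither says so nor gives a maximum time outside 2 to 8°C against which to judge a delayed parcel.

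The conclusion on the ranges rests only on the two texts and a unit conversion. The exposure of 0 to 26 of 39 doses per patient (0 to 300 shipments) assumes 6-month supplies, all 150 patients remaining in the study, and a courier share anywhere from none to all. Whether room-temperature transit is acceptable for the product is left open, because the prescribing information is not part of the documents. The point is confined to transit. It does not cover storage at home and does not touch the endpoints, sample size or analysis.

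**What to change.** 1. In Appendix item 2, replace *at all times* with one transit temperature range and a maximum time outside 2 to 8°C, both taken from the prescribing information cited in A.3.
2. In item 4, condition the packs to match that range.
3. In B.8, cross-reference this range and time limit as the temperature requirement for the patient leg, so that the rule on use has a defined meaning there.
4. In item 7, make the existing call before first use of the supply and have it confirm that delivery fell within the limit. A supply that failed is replaced and not used.

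The cost is wording in B.8 and in items 2, 4 and 7, one extra question in a call already required, and occasional replacement supplies. A single-use temperature indicator in the box would be a reasonable option but is not needed for the correction. Design, endpoints, sample size and analysis are unchanged.
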